To evaluate whether rt-fMRI neurofeedback improves the ability to increase reward-related brain activation in individuals with and without ND. To address this question we will compare individual's BOLD response to: baseline (passive viewing of reward images), Pre-Test (view personalized and non-personalized non-drug cues prior to neurofeedback), Training (view personalized, non-drug cues while receiving neurofeedback), and Post-Test (view personalized and non-personalized non-drug cues following neurofeedback). In this manner we will characterize and quantify individual's ability to increase brain activity to personalized, non-drug rewarding stimuli.

To examine the relationship between activation of reward-related regions via neurofeedback and dopamine availability (as assessed genetically). To assess this question we will first send the genetic data to the Duke University DNA Analysis Facility for analysis. Once the SNPs and VNTRs have been analyzed we will correlate individual's level of dopaminergic related genetic material (e.g., COMT, DAT) to their ability to regulate reward-related activation during the task.

To examine the effects of neurofeedback on clinically relevant outcomes, including reward responsivity and smoking related behaviors. To assess this we will examine participants brain activity during the Passive Viewing Task and the ReAcT. We will also perform a simple Delay to Smoking Assessment where we will measure (in minutes) how long participants take to smoke their first cigarette. We will also measure how many cigarettes they smoke during their break. We will correlate individual's ability to increase brain activation to personalized, non-drug cues in the ReAcT with both their time to initiate smoking and the number of cigarettes smoked.

Data & Safety Monitoring

Summarize safety concerns, and describe the methods to monitor research subjects and their data to ensure their safety, including who will monitor the data, and the frequency of such monitoring. If a data monitoring committee will be used, describe its operation, including stopping rules and frequency of review, and if it is independent of the sponsor (per 45 CFR 46.111(a) (6)).

Only participants meeting all inclusion and no exclusion criteria will be enrolled in the study. Pre-screening for appropriateness to undergo MRI scanning will be completed prior to the procedure to make sure to exclude participants who are not safe to undergo MRI scanning such as people who have metal implants, non-removable piercings, a copper IUD, have worked with metal, or had an eye injury involving metal. Protocols are in place for participants who may experience anxiety or panic attacks during study assessments. Urine pregnancy test is required for each female prior to scanning procedure. The test must be negative in order to proceed. The PI and her study team will review appropriateness of participants for the study.

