Prior to coming to a screening visit, all potential participants will undergo a phone pre-screening using an IRB approved phone script to pre-identify potentially eligible participants and to potentially decrease screen fail rate. These interested potential participants call or email the site in response to advertisements or provide their contact information via the internet (e.g, Facebook ad). The pre-screening will take place via phone. Participants who pass the pre-screening will complete some or all of the following visits: Screening, Camera Return Visit, Real-Time Neurofeedback Visit, Follow-up Phone Calls/Debriefing.

Screening Visit:

Participants with nicotine dependence who pass the pre-screen will come to the lab at Duke to complete additional screening. All participants will undergo informed consent. MRI participants will complete a urine drug screen. Participants who pass the urine drug screen (results are provided immediately) may complete questionnaires on REDCap assessing mood, reward processing, and smoking behaviors. We may also ask individuals with ND to complete a carbon monoxide (CO) breath test. If individuals fail to pass, they will be offered the opportunity to smoke and come back to get tested again. If they fail a second time, they will be excluded from the study. We may also ask individuals if they have consumed marijuana within the last 24 hours. If they have, the session will end and they will be asked to complete the screening visit another time if they would like. Additionally, we may ask participants to provide us with the names and contact information for up to 4 individuals who we can ask to confirm smoking status. We may also perform a cotinine test to verify smoking status. Also, individuals may fill out a MRI safety screening form confirming they are eligible to be scanned for the MRI visit.

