Eligible participants will be scheduled for an fMRI and/or EEG session to assess and measure the ability to self-activate reward-related regions. The fMRI session will be conducted at either the Duke-UNC Brain Imaging and Analysis Center (BIAC) and/or the UNC Biomedical Research Imaging Center (BRIC), where we have secured a contract for neuroimaging data acquisition. Female participants will have a urine pregnancy test prior to fMRI scanning; the test will be verified to be negative in order to proceed with the scanning session. The EEG sessions will take place in private testing space in the Levine Science Research Center or the BIAC. The real-time neurofeedback visit will be scheduled within 60 days of the screening visit. We are using this window to allow for limited availability of the MRI scanner as well as flexibility to find an ideal time for the participant (e.g., evening or morning scan time). MRI participants may fill out a screening form confirming they are still eligible to be scanned or review a completed screening form if filled out at the screening visit. A carbon monoxide breath test may also be conducted but will not be used in determining eligibility.

Participants may complete some or all of the following tasks: Reward Activation Task, Passive Viewing Task, and Reward Learning Task. All of these tasks aim to assess how adults can learn to interact with neurofeedback provided from an fMRI or EEG system. The tasks vary slightly from each other in terms of stimuli used (personalized pictures, images provided by the experimenters, feedback display, etc.). It may be possible that we will not be able to get a good EEG or fMRI signal for some participants, based on equipment error or head size. If this occurs, participants will be debriefed and paid for their time. We will be sure to emphasize there was no error on the participant's part, and that sometimes the signal is difficult to acquire for a variety of reasons.

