Scale (20 item), the SHAPS, the DEWL, the BVAQ English Questionnaire (40 item), Personal History Form, CES-D, Difficulties in Emotion Regulation Scale (36 item), the General Self-Efficacy Scale, the Fraser Imagery Questionnaire (10 item), the Spontaneous Use of Imagery Scale (12 item), and the State and/or Trait Anxiety Inventories (20 items each) will index state and trait personality measures. We may additionally collect the following smoking-related measures: the Wisconsin Smoking Withdrawal Scale (28 item), the MNWS (may be administered pre and post neurofeedback session), Contemplation Ladder, the Questionnaire of Smoking Urges58 (may be administered pre and post the neurofeedback session). We estimate that completion of these questionnaires will take approximately 35 minutes.

Self-report: participants will be asked to self-report strategies they used to regulate their brain activation. They may be asked to write them down or record them using software such as Audacity (see Pre-Session Questionnaire, Post-Session Questionnaire, and SB Post Session Questionnaire Final as examples). Participants may also be asked to rate their levels of motivation, arousal, enthusiasm, etc. throughout the experiment via making responses on a button box or response dial.

Smoking biomarker: To verify smoking status for nicotine dependent participants, we will measure expired air CO via a handheld monitor (e.g., Vitalograph). To ensure recency of smoking that is sufficient to produce detectable levels of CO, participants with CO levels below the required cutoff will be permitted to smoke one of their own cigarettes outside the lab prior to providing a second breath sample if they choose to do so.

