Genetic measures: Saliva may be collected. If so, we will use a commercially available kit from Oragene (<http://www.dnagenotek.com/ROW/products/OG500.html>). This is a very simple procedure in which participants deposit saliva into a plastic tub. It is non-invasive and takes a few minutes. The tubes will be de-identified and labeled by participant ID number. They will be stored in a locked cabinet inside secure office space. These saliva samples are stable stored at room temperature and can be kept in room temperature storage for up to 5 years. Once data collection is complete, we will send them to the Duke University DNA Analysis Facility for one time analysis. We will examine genetic markers related to dopamine function. Examples include both SNPs (e.g., DRD1, DRD2) and VNTRs (e.g., DAT, MAOA).

Follow-up Phone Call/Debriefing:

For ND individuals: participants may be called and/or sent a link to a REDCap survey 1 day, 1 week, and/or 1 month following the MRI visit to assess if there is any change in their smoking behavior following study participation. We will ask participants if they have modified their smoking behavior in any way (e.g., # of cigarettes smoked, craving, etc, see Contemplation ladder and rtNic.01 Follow up Questionnaire as examples). During the last phone call, we will debrief participants regarding which group they were in (Veridical Feedback Group or Noise Control Group) and answer any remaining questions they have about the study.

Selection of Subjects

List inclusion/exclusion criteria and how subjects will be identified.

Inclusion Criteria:

18-55 years of age

In good general health

Male or Female

For ND individuals: Self-reported smoking \geq 5 combustible cigarettes per day

For ND individuals: Afternoon expired CO concentration of \geq 8 ppm

For ND individuals: Is willing and able to abstain from smoking for a few hours

Exclusion Criteria:

Current chronic/significant medical condition

Current or past 6 month use of prescription medications for psychiatric conditions (e.g., depression, anxiety)

Current or past 6 month diagnosis of anxiety, bipolar disorder, depression, OCD, schizophrenia, psychosis, or personality disorder.

Current substance abuse or dependence or history within the last 6 months (other than nicotine for ND individuals)

For ND individuals: Currently on nicotine replacement therapy

For ND individuals: Individuals who role their own cigarettes

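### Nicotine deprivation at the neurofeedback visit is neither standardised nor required to be measured, so it can confound the unadjusted correlation of brain activation with later smoking

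*Combined protocol and SAP*

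**What the plan says.** All references are to the combined protocol and SAP.

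- **Abstinence.** The only text is an entry under Inclusion Criteria: "For ND individuals: Is willing and able to abstain from smoking for a few hours". No section says when abstinence starts, how long it lasts or how it is checked, and none asks for the time of the last cigarette before the session. Under Real-Time Neurofeedback Visit, the session may be in the morning or the evening, up to 60 days after screening.
- **Measures on the day.** The same section says: "A carbon monoxide breath test may also be conducted but will not be used in determining eligibility". For the MRI or EEG visit, the questionnaire section says: "We may additionally collect the following smoking-related measures: the Wisconsin Smoking Withdrawal Scale". It goes on to the MNWS and the Questionnaire of Smoking Urges, all permissively worded. Craving self-report under Delay to Smoking Assessment is also optional. The Passive Viewing Task does ask for intermittent craving ratings in firm wording, but participants do only some or all of the tasks.
- **CO elsewhere.** Under Smoking biomarker: "To verify smoking status for nicotine dependent participants, we will measure expired air CO via a handheld monitor". No visit is named, and a participant below the cutoff may smoke and be retested. Under Screening Visit: "We may also ask individuals with ND to complete a carbon monoxide (CO) breath test". Inclusion Criteria nevertheless require an afternoon CO of at least 8 ppm.
- **Dependence severity.** The Fagerström test (FTND) is among the questionnaires that may be completed at screening.
- **Analysis.** Under the aim on clinically relevant outcomes, Data Analysis & Statistical Considerations correlates the ability to increase activation to personalised non-drug cues "with both their time to initiate smoking and the number of cigarettes smoked". It names no covariate, does not define the activation score, and names no comparison of these two outcomes between feedback groups.

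**The concern.** Time since the last cigarette could plausibly affect both how a person's reward regions respond or can be regulated and how soon and how much that person smokes afterwards. Dependence severity could do the same. The plan lets deprivation vary, does not guarantee a record of it, and then relates the two quantities without adjustment.

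Randomisation does not answer this. What is randomised is the type of feedback. The exposure in this analysis is each person's achieved activation, which arises after assignment and is not itself randomised. Deprivation can be balanced between the two groups and still produce a correlation across people, whether pooled or within a group.

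The correlation sits under an aim about the effects of neurofeedback, and delay and cigarette count are the only smoking behaviours the analysis section names for it. A crude association could therefore be read as a clinical effect when deprivation produced it, or a real association could be hidden. Deprivation that is not recorded on the day cannot be recovered at analysis.

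**Working it through.** **No figure to reproduce.** The documents give no alpha, power, effect size or expected correlation for this analysis.

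**Inputs.** From the document: up to 100 ND participants. This is a ceiling, because the delay assessment is optional and depends on time and space, and not everyone need do the ReAcT. Assumed: a two-sided 5% test; n = 50 as a smaller case; a, the correlation of deprivation with the activation score; b, its correlation with delay.

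**Step 1: induced correlation.** If activation and delay have no direct link, their partial correlation given deprivation is zero. The numerator of the partial correlation is r − ab, so r = a × b.

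**Step 2: chance of a significant result.** With Fisher's z and m = atanh(r) × √(n − 3), the rejection probability is Φ(m − 1.96) + Φ(−m − 1.96). For a = b = 0.4 and n = 100: r = 0.16, atanh(r) = 0.1614, √97 = 9.849, m = 1.590. This gives Φ(−0.370) + Φ(−3.550) = 0.356.

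| a | b | r = ab | n = 50 | n = 100 |
|---|---|---|---|---|
| 0.2 | 0.2 | 0.04 | 6% | 7% |
| 0.3 | 0.3 | 0.09 | 10% | 14% |
| 0.4 | 0.4 | 0.16 | 20% | 36% |
| 0.3 | 0.5 | 0.15 | 18% | 32% |
| 0.5 | 0.5 | 0.25 | 42% | 71% |

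Simulation with 5,000 runs agrees: for 0.3/0.3, 9.8% (n = 50) and 14.2% (n = 100); for 0.5/0.5, 41.4% and 70.8%. For scale, the correlation detectable with 80% power is tanh((1.96 + 0.84)/√(n − 3)), which is 0.28 at n = 100 and 0.39 at n = 50.

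**Step 3: sign.** The rates above are two-sided. If a and b have the same sign, the induced correlation is positive and looks like benefit (more activation, longer delay). If the signs differ, it is negative: a true benefit is masked, and false positives in the benefit direction fall below the nominal 2.5%.

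**Step 4: the activation score.** Suppose deprivation D adds c₁D to the pre-test response and c₂D to the post-test response. A post-minus-pre score contains (c₂ − c₁)D. A constant effect (c₁ = c₂) cancels. An effect on regulation or learning (c₁ ≠ c₂) does not.

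**Step 5: what adjustment achieves.** Let the recorded measure have reliability ρ (its squared correlation with true deprivation). The residual partial correlation is ab(1 − ρ)/√((1 − a²ρ)(1 − b²ρ)). For a = 0.3, b = 0.5, n = 100:

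| ρ | residual r | rejection rate |
|---|---|---|
| 0 (no adjustment) | 0.15 | 32% |
| 0.3 | 0.11 | 20% |
| 0.5 | 0.08 | 13% |
| 0.8 | 0.035 | 6% |
| 1 | 0 | 5% |

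**The case against.** The strongest reply has four parts.

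**Proxies exist.** The withdrawal, urge and craving measures could all stand in for deprivation, and the Smoking biomarker text is firm that CO will be measured. A reader might infer that the plan collects nothing on deprivation; that is not so. The gap still stands. The session-day scales are optional, the craving ratings depend on an optional task, the firm CO statement concerns smoking status and names no visit, and the analysis uses none of them. A CO value taken after an invited cigarette does not measure deprivation at a later session.

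**Confounding is not demonstrated.** This is correct. The documents give no data linking deprivation to activation or to delay, and with weak links the error rate stays close to nominal. The 71% needs both the strongest assumed links and the full 100 participants. At an assumed n = 30, links of 0.3/0.3, 0.4/0.4 and 0.5/0.5 give about 8%, 13% and 26%.

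**The score may remove it.** The analysis concerns the ability to increase activation, and the ReAcT has identical pre-test and post-test runs. A change score would cancel a constant effect. This narrows the concern but does not close it, because the score is undefined and an effect on learning survives.

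**The design is randomised.** A comparison of the two feedback groups would be balanced on deprivation in expectation, and nothing here impugns it. The plan names no such comparison for delay or cigarette count.

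Leaving session-day CO out of eligibility is not a defect in itself; the issue is only that it need not be recorded and is not used in the analysis.

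**Conclusion.** The concern holds as a possibility that the plan leaves open: deprivation and dependence severity can confound the stated correlation. The documents do not support saying that they do confound it, that the bias would favour neurofeedback, or that any particular error rate is to be expected. Those stronger readings need links that the documents do not give.

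Under the assumed range of 0.2 to 0.5 for both links, the two-sided false-positive rate runs from near nominal (6% to 7%) to 42% at n = 50 and 71% at n = 100. This also assumes a 5% test, no direct association, and an activation score that does not cancel the deprivation effect. The change is worth making because it is cheap and cannot be made afterwards.

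**What to change.** - **Measurement.** On arrival at the neurofeedback visit, record the time of the last cigarette and expired CO in every ND participant. Collect the FTND in all of them. The arrival measures precede training, so adjusting for them does not remove a training effect.
- **Analysis.** Define the activation score. Replace the crude correlation with a regression or partial correlation adjusted for time since last cigarette, CO and FTND, and report the crude correlation alongside.
- **Feedback group.** Show the estimate with and without group as a covariate rather than adding it by default. Adjusting for group removes the between-group variation in activation, which may be part of the signal of interest.
- **Consistency.** The sponsor should reconcile the CO and abstinence wording across Screening Visit, Real-Time Neurofeedback Visit, Smoking biomarker and Inclusion Criteria. No eligibility or abstinence rule is proposed here.

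**Cost.** One question, a short breath test on a monitor already planned, completion of a listed questionnaire, some SAP wording and a few degrees of freedom. Some confounding will remain if the measures are imprecise: 13% rather than 5% in the illustration with reliability 0.5.

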Self-activation of Reward-related Brain Regions in Individuals with and without Nicotine Dependence

NCT03170258

Document Date: April 29, 2024

Purpose of the Study

- To assess the ability of adults with and without nicotine dependence (ND) to activate reward-related brain areas (e.g., ventral tegmental area (VTA), striatum, prefrontal cortex (PFC)).
- To evaluate whether real-time functional Magnetic Resonance Imaging (rt-fMRI) and/or real-time electroencephalography (EEG) neurofeedback improves the ability to increase reward-related brain activation in individuals with and without ND.
- To examine the relationship between activation of reward-related regions via neurofeedback and dopamine availability (as assessed genetically).
- To examine the effects of neurofeedback on clinically-relevant outcomes, including reward responsivity and smoking-related behaviors.

Background & Significance

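### The smoking analysis under the fourth study purpose correlates brain activation with two smoking-break measures; it names no comparison of the randomised groups and leaves out the optional follow-up, urge and withdrawal data

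*Combined protocol and SAP*

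**What the plan says.** Purpose of the Study lists four purposes. The last is "To examine the effects of neurofeedback on clinically-relevant outcomes, including reward responsivity and smoking-related behaviors".

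Design & Procedures describes the smoking measures, all for ND participants and all optional:

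- **Delay to Smoking Assessment.** Minutes to the first cigarette and number of cigarettes may be recorded after the session, if time and space permit.
- **Questionnaire measures.** Among the scales for the MRI or EEG visit, the MNWS "may be administered pre and post neurofeedback session". The Questionnaire of Smoking Urges likewise "may be administered pre and post the neurofeedback session".
- **Follow-up Phone Call/Debriefing.** Contact by telephone or online survey is possible at one or more of three times after the MRI session (1 day, 1 week, 1 month). The reason given is "to assess if there is any change in their smoking behavior following study participation". Group assignment is disclosed during the last call.

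The Reward Activation Task (ReAcT) section says participants may be randomised to Veridical Feedback or Noise Control, and treats the Noise group as an essential control.

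Data Analysis & Statistical Considerations restates the purpose ("To examine the effects of neurofeedback on clinically relevant outcomes, including reward responsivity and smoking related behaviors") and gives its analysis: brain activity in the Passive Viewing Task and the ReAcT, minutes to first cigarette, cigarettes smoked in the break, and the correlation of ReAcT activation with those two break measures.

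**The concern.** The purpose asks what neurofeedback does to smoking. The design has the tool to answer that, a randomised control group, but the smoking analysis does not use it. Activation is measured after randomisation and is not itself randomised. People who activate more strongly may also differ in dependence, motivation or general reward sensitivity, and any of these could produce the correlation with neurofeedback doing nothing.

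The measures closest to the aim are also left out. The follow-up contacts are there specifically to look at change in smoking, and the urge and withdrawal scales may have a value before and after the session. If the plan is followed as written, the fourth purpose yields a brain-behaviour association from one session and no randomised estimate for smoking or craving. If the omitted data are analysed anyway, the outcome, time point and method will have been chosen after the data were seen.

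**Working it through.** **1. Measures against analysis.**

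| Smoking measure | Status in procedures | In the stated analysis? | Compared by arm? |
|---|---|---|---|
| Minutes to first cigarette | optional | yes, correlated with activation | no |
| Cigarettes in the break | optional | yes, correlated with activation | no |
| Urges scale, pre/post | optional | no | no |
| MNWS, pre/post | optional | no | no |
| Smoking reports at 1 day, 1 week and/or 1 month | optional | no | no |

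The analysis section does refer to within- and between-subject analysis, but that sentence governs the fMRI time series, not the smoking outcomes. The cigarette count in the correlation is the one from the break, not from follow-up.

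**2. Why the correlation does not answer the question.** Let A be activation and Y a smoking outcome, with two equal arms. Then

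cov(A, Y) = average within-arm cov(A, Y) + (Δ_A × Δ_Y) / 4,

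where Δ_A and Δ_Y are the differences between arm means. Only Δ_Y is the effect of neurofeedback on smoking. If Δ_Y = 0, the second term vanishes, yet the correlation is non-zero whenever A and Y are related within arms. If Δ_Y is real but Δ_A is near 0, the second term also vanishes and the effect is missed. Precision is a separate matter: by Fisher's z, the correlation could detect about r = 0.28 with 100 ND participants or 0.39 with 50 (80% power, two-sided 0.05).

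**3. What an arm comparison could detect.** The plan states no alpha, power, allocation ratio or dropout, so there is no figure to reproduce. The only input from the documents is the maximum of 100 ND adults (Design & Procedures). Assumed: 1:1 allocation, so at most 50 per arm; complete data; two-sided 0.05; 80% power.

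Normal approximation: d = (1.960 + 0.842) × √(2/n). At n = 50 this is 2.802 × 0.200 = 0.560. The t-test calculation gives slightly larger values:

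| ND per arm | Detectable d, unadjusted |
|---|---|
| 50 | 0.57 |
| 40 | 0.63 |
| 30 | 0.74 |
| 20 | 0.91 |

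Baseline adjustment multiplies d by √(1 − r²). From 0.566 at 50 per arm:

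- r = 0.5: 0.566 × 0.866 = 0.49
- r = 0.7: 0.566 × 0.714 = 0.40
- r = 0.8: 0.566 × 0.600 = 0.34

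The values of r are assumptions.

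**4. Multiplicity.** If tests were independent and unadjusted at 0.05, the familywise error would be 1 − 0.95³ = 14% for three tests and 1 − 0.95⁵ = 23% for five. At Holm's first step over three outcomes the level is 0.05/3 = 0.0167, and the detectable d at 50 per arm rises from 0.57 to about 0.66.

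**The case against.** The strongest reply is that this is mainly a mechanistic study. Three of its four purposes concern brain activation and dopamine genetics, wishing to quit is not an entry criterion, no direct benefit is expected, and two smoking behaviours are analysed. Follow-up smoking could fairly be exploratory. That stands as an argument about rank, and secondary or exploratory status meets it. It does not rescue the correlation, because the stated purpose is an effect.

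Three stronger readings are tempting and are not supported:

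- **A reader might infer that a full follow-up dataset will be collected and left unanalysed.** Every measure is worded as optional, and the three follow-up times are joined by and/or. Data may not exist for many participants.
- **A reader might infer that follow-up smoking has a ready baseline.** Cigarettes per day is self-reported for eligibility, but the follow-up asks whether smoking has been modified, and its questionnaire is cited only as an example. Nothing shows that it records cigarettes per day in the screening form. Only the MNWS and the Urges scale are described as possibly given before and after the session.
- **A reader might take 50 per arm as the expected size.** The 100 is an upper limit, participants may do only some tasks, randomisation is itself worded as optional, and follow-up is timed from the MRI visit, which leaves EEG-only participants undefined.

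**Conclusion.** The concern holds in this form: the analysis for the fourth purpose contains no randomised comparison on any smoking outcome, and it omits the optional follow-up, urge and withdrawal measures. As written it cannot estimate an effect of neurofeedback on smoking. This is a choice of method, not just missing detail, and it should be corrected.

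The case for changing it rests on the mismatch between aim and analysis, not on the power figures. Those are a best case. Even then only moderate differences are detectable, and with 20 to 30 per arm only large ones, so estimates with confidence intervals will matter more than tests. The benefit of baseline adjustment depends on correlations the documents do not give.

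**What to change.** Add to the analysis for the fourth purpose, in ND participants randomised in the ReAcT, comparisons by randomised arm of:

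1. time to first cigarette and number of cigarettes in the break;
2. post-session Urges and MNWS scores, by ANCOVA on the pre-session score;
3. cigarettes per day at 1 month as the main follow-up outcome, adjusted for screening cigarettes per day, with the 1-day and 1-week values in a repeated-measures model using all available data.

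Keep the correlation with activation as a supporting analysis. Label the new comparisons secondary with Holm adjustment, or exploratory, and state how missing follow-up is handled.

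Three changes to data collection are needed to make this work. Give these measures to all ND ReAcT participants where feasible. Ask cigarettes per day in the same form at screening and follow-up. Record the smoking report before group assignment is revealed in the last call. The plan should also say when follow-up starts for EEG-only participants, and reconcile the Delay to Smoking Assessment, which is optional in the procedures but definite in the analysis section.

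Cost: analysis wording, a few minutes of questionnaires already listed, more secondary tests, and up to three follow-up contacts per ND participant, with calls paid at $35 per hour under Subject Recruitment and Compensation.
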